2.1.2 Secondary objectives

The secondary objective is to assess all relevant device and subject demographic characteristics, procedural events through hospital discharge and short-term outcomes, up to 1 year postimplant.

2.2 Overall study plan

Study main characteristics are described below. Please refer to the CIP for additional details.

- Prospective, interventional, multi-center study.
- Single-arm: subject implanted with Perceval aortic heart valve.
- Minimum of 75 asymptomatic and symptomatic subjects with evaluable 4D CT scans.
- Approximately 11 investigational sites where the devices are commercially available.
- Study duration: approximately 3 years (24 months for the enrollment phase and 1 year for the follow up phase).
- Blinding of CT scan imaging: (i) asymptomatic subjects and principal investigators (PIs) blinded from the CT imaging and Core Laboratory (Lab) findings; (ii) symptomatic subjects and the PI can be unblinded to CT imaging results; (iii) Core Lab blinded to subject status.
- Main assessments: (i) subject inclusion and implant data; (ii) hospital discharge (or 30-days after implant); (iii) anticoagulation (ACT) or dual antiplatelet therapy (DAPT) discontinuation (or Planning) visit (iv) first CT scan at minimum of 1 month after the discontinuation of ACT/DAPT; (v) second CT scan within 1 year post-implant for subjects in which reduced leaflet motion was previously detected; (vi) 1 year post-implant.

The visits are planned as reported in Figure 1

Figure 1: Schedule of Study Procedure

Procedure	Pre- Implant / Implant Data	Hospital Discharge	ACT / DAPT Discontinuation (or Planning) Visit	1 st CT-Scan Follow- up Visit	Reduced Leaflet Follow-Up (2 nd CT- Scan)	1 Year Follow- Up	Unscheduled Visits
Applicable Subjects	All Subjects	All Subjects	Subjects on ACT / DAPT	All Subjects	Subjects with Reduced Leaflet Motion on 1st CT Scan	All Subjects	Subjects with reduced leaflet function symptoms or other condition needing study related Follow-up
	After	≤ 30 days of Implant	1 – 6 mo.	Non-ACT/DAPT Pts. 30 days after Hospital Discharge (+ 60 day window)	6 – 10 mo.	1 year after the day of	At Discretion
	Successful Implant	ul (before the Po	Post-Implant (3 mo. preferred)	ACT/DAPT Pts. 30 days after ACT/DAPT Therapy discontinuation (+ 60 day window)	6 – 10 mo. Post-Implant	surgery (± 30 day window)	of Investigator

Study: APR002 BELIEVE

2.3 SAMPLE SIZE CALCULATION

A sufficient number of subjects will be enrolled in this study to allow a minimum of 75 evaluable CT scans for the primary endpoint. Evaluable scans are those where a determination of normal or abnormal leaflet motion is possible. Considering an attrition rate of 15% of subjects, the sample size targeted for enrollment is approximately 88 subjects.

A sample size of 75 evaluable CT scans produces an Exact two-sided 90% CI with a width lower than 13% when the sample proportion is lower than 10% (evaluation calculated using PASS software, version 13).

2.4 RANDOMIZATION

Not applicable.

3 DOCUMENT AND CHANGE HISTORY

3.1 CHANGES IN ANALYSIS COMPARED TO CLINICAL INVESTIGATIONAL PLAN

No changes in the analysis have been applied compared to protocol.

Although not specified in the CIP, "Per-Protocol" population has been included in this SAP as population analysis set.

3.2 SAP AMENDMENT RATIONALE AND CHANGE HISTORY

COPYRIGHT LIVANOVA. ALL RIGHTS RESERVED. MAY NOT BE REPRODUCED WITHOUT PERMISSION. ALL HARD COPIES SHOULD BE CHECKED AGAINST THE CURRENT ELECTRONIC VERSION WITHIN MASTERCONTROL PRIOR TO USE AND DESTROYED PROMPTLY THEREAFTER. ALL HARD COPIES ARE CONSIDERED UNCONTROLLED DOCUMENTS.

LN-GLB-CLN-TEM-0033 rev1 Page 6 of 42

Version	Date	Section(s)	Description of modifications	
1.00	14MAR2018	All	Initial Release.	
			SAP has been amended following the:	
2.00	13MAY2019	All	 Protocol Amendment Version No. B dated on 05 Dec 2018: The study was initially designed with three cohorts of valve types to be analyzed: Perceval, SOLO Smart, and CROWN PRT. In an effort to focus the research to the Perceval device, the other cohorts (SOLO/CROWN) are being removed from the research study. The subjects that have received one of the two devices prior to removal from the study will be followed and presented as a subcategory in safety tables but will not be included in the endpoint analysis. Additionally, with this change the total number of subjects required for the study is approximately 88 which should yield 75 evaluable CT Scans. CRF specification Amendment Version 2 dated on 09 May 2019. 	
2.00	13MAY2019	All	Removal of Crown PRT and Solo Smart references.	
2.00	13WA12013	All	Minor editorial changes applied to increase SAP clarity.	
			Study sample size reconsidered based on the following changes:	
2.00	13MAY2019	2.3, 5.2, 10, 11	 Study cohort changed from three to one. The study is descriptive in nature, aiming at describing the risk of reduced leaflet motion as such it is considered non-confirmative and no multiplicity adjustment will be applied to the inferential statistical methods that will be presented. Confidence levels updated to 90% rather than 95%. Expected acceptable confidence interval width updated to be 13% rather than 8.3%. 	
			 Statistical two-sided confidence interval calculation to compute the sample proportion (Reduced Leaflet Mobility) updated to be based directly on the Exact Binomial distribution rather than Normal approximation (Wald). 	
2.00	13MAY2019	5.3, 18.13	Subgroups analysis updated to remove the classification by valve.	
2.00	13MAY2019	6.4, 7.3, 18.13	Section updated to include the reference at the primary endpoint-related deviations as reported in the Risk Based Study Management Plan.	
2.00	13MAY2019	13.1	Sections updated to specify where a SAE relationship will be further judged by Sponsor or Clinical Events Committee (CEC), only the final assessment will be analyzed by means of the following judgment order: 1. Site/CoreLab, 2. Sponsor, 3. CEC.	
2.00	13MAY2019	10.4	Primary Analysis updated to calculate the Exact 2-sided 90% confidence limits, fo the reduced leaflet motion proportion, based on the Binomial distribution.	
2.00	13MAY2019	10.5	Section updated to clarify the procedures for the multiple imputation of missing data at first CT scan visit.	
2.00	13MAY2019	13	 Safety analyses updated to: Include the enrollment occurrence (subjects enrolled at implant/after implant) stratification. Remove the reference to treatment emergent adverse events since these are not of main interest in device studies. Replace reference to "System Organ Class (SOC)" and "Preferred Term (PT)" with "SAE general category" and "SAE term", respectively. 	
2.00	13MAY2019	18.6	Visit windows clarified as per Protocol Version B.	

COPYRIGHT LIVANOVA. ALL RIGHTS RESERVED. MAY NOT BE REPRODUCED WITHOUT PERMISSION. ALL HARD COPIES SHOULD BE CHECKED AGAINST THE CURRENT ELECTRONIC VERSION WITHIN MASTERCONTROL PRIOR TO USE AND DESTROYED PROMPTLY THEREAFTER. ALL HARD COPIES ARE CONSIDERED UNCONTROLLED DOCUMENTS.

LN-GLB-CLN-TEM-0033 rev1 Page 7 of 42

4 OVERVIEW OF PLANNED STATISTICAL ANALYSIS

4.1 MAIN STATISTICAL ANALYSIS

Main statistical analysis will be performed after all evaluable subjects have completed the first CT scan at expected 1-6 months post-implant.

Study: APR002 BELIEVE

4.2 FINAL STATISTICAL ANALYSIS

Final analysis will be performed after all enrolled subjects have completed the study (1 year visit), and the data has been hard locked. The results of the final analysis will be the basis for the integrated Clinical Study Report (CSR).

4.3 OTHER STATISTICAL ANALYSES

Progress annual report may be prepared for eventual sending to the study team for internal evaluations of the study progress.

Specific statistical analysis may be provided to regulatory agencies upon request. In addition, internal evaluation could be requested during the study after assessing a reasonable number of subjects with results on the first CT scan at 1-6 months post-implant (i.e. every 50 subjects with the first CT-scan evaluation).

The Sponsor may also perform comparisons with previous studies in the same indication by means of meta-analytic approaches also using network meta-analyses, when required. More details will be presented in an ancillary SAP detailing this and any other exploratory analyses.

Additional statistical analyses may be run after the completion of the final analysis. In that case, an addendum of this SAP will be created describing the analyses to be performed.

5 Analysis convention

5.1 GENERAL PRINCIPLES

The statistical analysis will be performed on the analysis study database with SAS version 9.4 or above (SAS Institute, Cary, N.C.).

If two or more of the analysis sets as defined in Section 6 coincide or the difference is less than 5%, presentations will only be prepared for the population less restrictive.

The default significant level will be 10%. Confidence Intervals (CIs) will be calculated at 90% confidence level and all tests will be two-sided, unless otherwise specified in the description of the analyses.

All the data collected and derived in the study will be presented in subject data listings.

5.2 DESCRIPTIVE STATISTICS

Descriptive statistics will be calculated using as reference the number of subjects in the relevant analysis population (any exception will be specified) according to the nature of the data as follows:

Study: APR002 BELIEVE

- Continuous variables: number of non-missing observations, arithmetic mean, standard deviation, minimum and maximum values, median and quartiles.
 - If there are less than 5 observations, only the number of non-missing observations, arithmetic mean, median, minimum and maximum will be presented.
- Categorical variables: number of non-missing observations (n), the number of missing and the relevant percentage on the analysis population, number and relative frequencies. If not defined otherwise, the percentage denominator will be the number of subjects with nonmissing information.
 - In case of subcategories, the relative frequencies will be calculated based on the subjects in the subcategory, in this case a footnote will be added explaining the different denominators.
- Time-to-event variables: number of non-missing observations (n), minimum, first quartile, median including 90% CI, third quartile, and maximum. For calculating the survival estimate 90% CI bounds the log-log transformed estimate of CI bounds will be used. Greenwood formula will be used to estimate the variance of the log-log transformation of the Kaplan-Maier estimator.

In addition, Kaplan-Meier estimates and plots will be provided with:

- o the respective number at risk and the Kaplan-Meier estimates at time points 1 month, 3 months, 6 months, 9 months and 1 year.
- o the median and its 90% Cl.
- o the Hazard Ratio (HR), its 90% CI and the relevant p-value, when applicable.

Subjects ongoing and who are free from event at the analysis cut-off date will be censored at the analysis cut-off date. Subjects who have discontinued without an event will be censored at the date of discontinuation.

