10.1.1. Summary Statistics

Standard summary statistics will be calculated for all study variables.

For continuous variables, statistics will include means, Standard Deviation, median, quartiles and range values. Categorical variables will be summarized using count and frequency distributions.

Survival data will be evaluated using Kaplan-Meier method. The degree of uncertainty will be expressed with 90% confidence limits. The 90% CI bounds for the cumulative freedom will be calculated per the method proposed by Greenwood. Comparison of curves among subjects groups (if any) will be performed with the log-rank test at the 0.10 two-sided level of significance. Nonparametric estimates at 1-year post-implant of the survivor function and instantaneous hazard rate will be reported by time-intervals.

The following outcomes will be evaluated by summary statistics at each available assessment:

Demographic, clinical and surgical characteristics

- Incidence of reduced leaflet motion, overall and in symptomatic and asymptomatic subjects
- NYHA functional classification data
- Hemodynamic performance
- Valve regurgitation

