11.5 Freedom from Valve Safety

The following mortality and morbidity outcomes will be analyzed by means of time to event methods:

all-cause mortality

COPYRIGHT LIVANOVA. ALL RIGHTS RESERVED. MAY NOT BE REPRODUCED WITHOUT PERMISSION. ALL HARD COPIES SHOULD BE CHECKED AGAINST THE CURRENT ELECTRONIC VERSION WITHIN MASTERCONTROL PRIOR TO USE AND DESTROYED PROMPTLY THEREAFTER. ALL HARD COPIES ARE CONSIDERED UNCONTROLLED DOCUMENTS.

LN-GLB-CLN-TEM-0033 rev1 Page 21 of 42

- valve re-intervention
- myocardial infarction
- structural valve deterioration
- moderate or severe valve regurgitation
- valve endocarditis
- valve thrombosis
- thromboembolic events
- hemolysis
- major bleeding
- pacemaker implantation

Cox's proportional hazards regression models (Cox 1972, Breslow 1975) will be performed including, one by one, the following covariates: age class [refers to "≥18 and <65" years], gender [refers to "male"], ethnicity [refers to "not Hispanic or Latino"], presence of subject risk factor at baseline [refers to "No"], , NYHA at baseline [refers to "Class I"], abnormality of ascending aorta or of aortic root at implant [refers to "No"], presence of aortic regurgitation measured by post-implant intraoperative TEE [refers to "No"], reduced leaflet motion at first CT scan [refers to "No"], including the subgroup defined in Section 5.3: concomitant procedures [refers to "without"], subject symptoms [refers to "asymptomatic"], ACT/DATP [refers to "off"], Core Lab evaluation [refers to "TEE"].

Study: APR002 BELIEVE

Hazard rate, and its 90% CI, will be reported for each covariate.

Proportional hazard assumption will be investigated for each time-dependent outcome. In case of non-proportional hazards, a Weibull model will be assumed as parametric form of the distribution of survival times.

An additional analysis will be performed in order to evaluate the time free from ACT/DAPT to primary endpoint (reduced leaflet motion) up 1 year post-implant. Kaplan-Meier estimates and plots of time to event after implant will be produced as in Section 5.2. Subjects will be included in the analysis starting from their stop date of ACT/DAPT until the first evaluation of leaflet motion.

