18.6 VISIT WINDOWS

Measurements will be assigned to visits according to the windows allowed in the Protocol and reported in Figure 2. These are defined in Section 5.4 and resumed below:

- Pre-implant/implant: during and after successful implant.
- Hospital Discharge: ≤30 days post-implant.
- ACT/DAPT discontinuation visit: 1-6 months post-implant.
- First CT scan visit: ≥30 days (+ 60 days) after discharge (for subjects discharged off ACT/DAPT) or after ACT/DAPT discontinuation (for subjects discharged on ACT/DAPT).
- Second CT scan visit: after the first CT Scan and 6-10 months post-implant.
- 1 year visit: 1 year ± 1 month post-implant.

Figure 2: Visit Window Guide

Visit Name	Calculate from:	Window Start Day	Window Stop Day
Pre-Implant / Implant Data	Enrollment date	- 90	0
Hospital Discharge (completed prior to actual discharge)	Implant date	0	30
ACT / DAPT Discontinuation or Planning Visit	Implant date 90 days after Implant date preferred	30	180
1st CT-scan Follow-up Visit (no ACT/DAPT)	Hospital Discharge date 30 days after Hospital Discharge preferred	30	90
1st CT-scan Follow-up Visit (DC on ACT/DAPT)	ACT / DAPT Discontinuation date	60	240
2 nd CT-scan (if needed) A minimum of 6 weeks after 1 st CT-scan	Implant date	180	300
1 year follow-up	Implant date	335	395

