18.7 CONVERSION OF TIME INTERVALS

If a time interval was calculated in minutes, hours or days and needs to be converted into months or years the following conversion factors will be used:

- 1 month = 30.4375 days
- 1 year = 365.25 days

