ENR population	 SCR flag= "Yes" and DXSTDAT2 not missing ("Implant Surgical Details" e-CRF) and existing Enrolled Date
SAF population	 ENR flag= "Yes", and DXPERF= "Yes" ("Implant Surgical Details" e-CRF)
PP population	As reported in the Believe Risk Based Study Management Plan.
Time to study	"Implant Surgical Details" e-CRF and "Study Termination" e-CRF
termination (months)	[DSSTDAT – DXSTDAT2 + 1] / 30.4375

COPYRIGHT LIVANOVA. ALL RIGHTS RESERVED. MAY NOT BE REPRODUCED WITHOUT PERMISSION. ALL HARD COPIES SHOULD BE CHECKED AGAINST THE CURRENT ELECTRONIC VERSION WITHIN MASTERCONTROL PRIOR TO USE AND DESTROYED PROMPTLY THEREAFTER. ALL HARD COPIES ARE CONSIDERED UNCONTROLLED DOCUMENTS.

LN-GLB-CLN-TEM-0033 rev1 Page 40 of 42

Time to event	"Implant Surgical Details" e-CRF
(months)	[Even date – DXSTDAT2 + 1] / 30.4375 Subjects ongoing and who are free from event at the analysis cutoff date will be censored at the analysis cut-off date. Subjects who have discontinued without an event will be censored at the date of discontinuation.
Age at Enrollment (years)	"Demographics" e-CRF and "Inclusion/Exclusion Criteria" e-CRF Age= [ICFDAT - BRTHDAT + 1]/365.25 As only month and year of birth are reported in the CRF, 1 st day of the month will be used for birth date.
Change from baseline	Test Value at Visit X - Baseline Value

Where

ACTDIDAT = "Date Subject Discontinued ACT/DAPT Therapy"

BRTHDAT= "Date of Birth"

CPAETERM= "Complications/Please specify if any of the following intraoperative complications occurred. /AE Term"

CPYN= "Was concomitant procedure performed?"

DIMODEL= "Valve Model"

DSDECOD= "Reason for Termination"

DSSTDAT= "Date of Study Termination"

DVDECOD= "Deviation Description"

DVICSPEC= "If Informed Consent, specify reason"

DXPERF= "Was the implant successful?"

DXSTDAT2 = "Date of Implant"

ICFDAT = "Informed Consent Date"

IEYN= "Met All Eligibility Criteria?"

COPYRIGHT LIVANOVA. ALL RIGHTS RESERVED. MAY NOT BE REPRODUCED WITHOUT PERMISSION. ALL HARD COPIES SHOULD BE CHECKED AGAINST THE CURRENT ELECTRONIC VERSION WITHIN MASTERCONTROL PRIOR TO USE AND DESTROYED PROMPTLY THEREAFTER. ALL HARD COPIES ARE CONSIDERED UNCONTROLLED DOCUMENTS.

LN-GLB-CLN-TEM-0033 rev1 Page 41 of 42

IMGTYPE= "Specify the imaging modality currently being used for the subject"

MHCVDAT = "If Myocardial Infarction, date"

MHSTDAT3= "If Stroke, date"

NY= "No/Yes"

SCDISCYN= "Was the subject discharged on anticoagulant and/or dual platelet therapy?"

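### For regurgitation and structural valve deterioration found by echo, the 1-year Kaplan-Meier value is read at 365.25 days, inside the day 335-395 window of the 1-year echo, so it depends on when that visit is booked

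*SAP*

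**What the plan says.** - **Outcomes.** SAP 11.5: "The following mortality and morbidity outcomes will be analyzed by means of time to event methods". The list of eleven includes "moderate or severe valve regurgitation" and structural valve deterioration.
- **Reading points.** SAP 5.2 gives "Kaplan-Meier estimates at time points 1 month, 3 months, 6 months, 9 months and 1 year". Protocol 10.1.1 adds that the "instantaneous hazard rate will be reported by time-intervals".
- **Time scale.** SAP 18.13 computes time to event from actual dates ("Even date – DXSTDAT2 + 1] / 30.4375"). SAP 18.7 sets "1 month = 30.4375 days" and "1 year = 365.25 days".
- **Visit window.** SAP 18.6: "1 year visit: 1 year ± 1 month post-implant". The window guide there and in Protocol 7.10 gives days 335 to 395 from implant.
- **Echo schedule.** Protocol 7.4, 7.6 and 7.9 plan a transthoracic echo for all subjects at discharge, the first CT visit and 1 year. Protocol 7.8 adds one at the second CT visit, for subjects with reduced leaflet motion only. Under Protocol 7.7 an echo may be captured at an unscheduled visit.
- **Censoring.** SAP 5.2 and 18.13 cover event-free subjects who are ongoing (cut-off date) and those who discontinued (discontinuation date). Subjects who completed the 1-year visit are not named.
- **Event date.** SAP 18.11 bases SAE onset on the SAE start date. No rule covers a finding first made at a scheduled echo.

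**The concern.** Regurgitation and structural deterioration often come to light because someone looks. The recorded date is then the date of the echo, not of onset. When the curve is read at a fixed day inside the window of the examination that supplies the findings, two things can happen:

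- A finding at a 1-year echo held after the reading point is not counted in the 1-year value, although the visit complied with the protocol.
- If event-free completers are censored on their visit date, the risk set drains across the window. Each finding made late in the drained period then carries a large weight.

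The first effect lowers the estimated event proportion and the second raises it. Freedom from valve safety events up to 1 year is a secondary endpoint, and for these components its value would depend partly on booking habits. The 3-, 6- and 9-month values and the interval hazards have a related weakness: scheduled-echo findings can only appear as steps at visit dates.

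**Working it through.** **1. The SAP's own reading point.** 12 × 30.4375 = 365.25 days, which agrees with SAP 18.7. The window 335-395 is 365 ± 30, or 61 days.

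**2. Days past the reading point.** With d = visit date minus implant date, SAP time is (d + 1)/30.4375. It exceeds 12 when d + 1 > 365.25, so d = 365 to 395. That is 31 of 61 days, or 50.8% (30 of 61, 49.2%, without the +1).

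**3. Share of 1-year visits past it, by timing.** The timings are assumptions, restricted to the window: uniform 51%; normal centred on day 365 (SD 10) 52%; on day 355 (SD 10) 17%; on day 375 (SD 10) 85%.

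**4. Expected Kaplan-Meier value at 365.25 days.** Take a true proportion q = 5%, all first seen and dated at the 1-year echo. Let w(d) be the share of visits on day d and R(d) the share still at risk. Then

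1 − S = 1 − ∏ [1 − q·w(d)/R(d)], over days with d + 1 ≤ 365.25.

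After each day R falls by w(d) if completers are censored at the visit, or by q·w(d) if they are censored after the window.

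Uniform visits can be checked by hand. With later censoring the result is 5% × 30/61 = 2.5%. With visit-date censoring the factors are 1 − 0.05/j for j = 61 down to 32. The sum of 1/j over that range is 0.669, so the result is about 1 − exp(−0.05 × 0.669) = 3.3%.

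| Visit timing | Censored at visit | Censored later | At risk at 365.25 days, of 88 (visit censoring) |
|---|---|---|---|
| Uniform | 3.3% | 2.5% | 45 |
| Centred day 365 | 3.2% | 2.4% | 46 |
| Centred day 355 | 8.0% | 4.1% | 15 |
| Centred day 375 | 0.8% | 0.75% | 75 |

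A simulation of 20,000 trials with 88 subjects, uniform visits and visit-date censoring averaged 3.3%. The share of findings past the reading point averaged 51%, but its 5th to 95th percentiles ran from 0% to 100% because so few events occur.

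**5. Some cases found earlier.** If half of the 5% is found before the 1-year visit, uniform visits with visit-date censoring give 4.2% instead of 3.3%.

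**6. Moving the reading point alone.** At the end of the window, with uniform visits and visit-date censoring, the product over all 61 days gives 21% for a true 5%. The SAP does not propose this; it shows only that a later reading day is no repair.

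**7. Earlier reading points.** 3, 6 and 9 months are days 91.3, 182.6 and 273.9. By the text of SAP 18.6, the first CT visit comes 30 to 90 days after discharge or after stopping ACT/DAPT. With discharge by day 30 and discontinuation on days 30-180, that is by day 120, or on days 60-270. The next scheduled echo is on day 335 or later, except for the second CT visit on days 180-300. The window guide gives 60 to 240 days after discontinuation instead; the two passages must be reconciled, because they determine when echo findings can arise.

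**The case against.** A reader might infer that half of the 1-year findings are lost, that freedom from events is overstated, and that the earlier time points reflect nothing but the calendar. The documents do not support any of these.

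- **Half** requires visits centred near day 365. No visit distribution is given.
- **Direction** is not fixed. Visits centred on day 355 with visit-date censoring give 8.0% for a true 5%, which understates freedom.
- **Censoring at the visit** is an inference. It is plausible, because the final analysis follows completion by all subjects and Protocol 8.2.1 has a dated termination form for completers, but it is not written. Dating the event at the echo is not written either: these outcomes are reported as SAEs and adjudicated.
- **Lost** is too strong. The findings miss one reading of the curve. They remain in the later part of the curve, the Cox models, the SAE summaries and, for regurgitation, the by-visit and shift tables of SAP 12.2.
- **Calendar only** is too strong. Unscheduled echoes can detect events, and first CT visits are staggered.

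The size in the table is also a worst case, because every case is placed at the 1-year echo. The pooled Perceval data in Protocol 2.3.1 suggest few events: major paravalvular leak 1.4% early and 0.3% late, and no structural deterioration. Major leak is not the same outcome, but 0.3% of 88 is about 0.26 cases. Protocol 10 calls the study descriptive, SAP 5.2 shows numbers at risk, and most of the eleven outcomes have a clinical date of their own.

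All of this stands and limits the point. It does not repair the 1-year Kaplan-Meier value for the two echo-detected components, which the by-visit tables leave unchanged.

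**Conclusion.** The point holds for the 1-year Kaplan-Meier value of moderate or severe regurgitation and structural valve deterioration. It rests on dating the event at the echo. The part that can bias the value upward rests also on censoring completers at the visit. Under the timings tested, 17% to 85% of 1-year findings come after the reading point, and about half do if visits centre on day 365. A true 5%, all first seen at the 1-year echo, is then estimated at about 1% to 8% with visit-date censoring, or about 1% to 4% with later censoring. The bias shrinks as more cases are found at earlier or unscheduled echoes. For these components the 3-, 6- and 9-month values and interval hazards largely, though not wholly, follow the visit schedule. The primary endpoint and the outcomes with a clinical onset date are unaffected. Severity is minor to moderate: a descriptive secondary endpoint with a cheap remedy.

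**What to change.** In SAP 5.2 and 11.5, for echo-detected components:

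1. Report the proportion affected at each echo visit and the cumulative proportion affected by the 1-year visit. Assign findings by the SAP 18.6 windows and use the exact binomial 90% CI of SAP 10.4. This replaces the Kaplan-Meier time-point values and interval hazards for these components. A finding on any of days 335-395 then counts at 1 year, and the true 5% of the example is recovered.
2. Label results by visit, not by day. The first CT visit is anchored to discharge or ACT/DAPT discontinuation and has no nominal day after implant.
3. State which date is the event date for a finding first made at an echo.
4. State the censoring date for subjects who complete the 1-year visit.
5. Keep Kaplan-Meier on actual dates for events with a clinical onset date, such as death, re-intervention, myocardial infarction, bleeding and thromboembolism.

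The cost is SAP wording and a simple derivation, with no new data. Exact echo dates go unused for these components, and subjects without a 1-year echo must be shown as missing, with the denominator given.
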